4.3 Risk-Benefit-Assessment

The Investigational Products (IPs) Sterofundin® ISO, Gelafundin® 4% and Sodium Chloride 0.9% are registered in Germany as well as in various European countries. The proposed use of the Investigational Products in the present study is in line with the registered SmPCs. Gelofusine® Balanced is also registered in Germany since December 2011. The active substance MFG is well-known in clinical routine in order to perform volume replacement intra- and postoperatively. Gelatine solutions have been marketed for more than 40 years by now. All ingredients of the new gelatine solution are well-known and there are already comparable gelatine solutions with comparable carrier solutions on the market.

Clinical studies with other balanced volume replacement products have shown the positive impact of the balanced concept on acid base status.

Most of the proposed measures and parameters (laboratory, clinical) are performed/obtained routinely and thus do not represent major additional burden to the patient. Study specific measurements require additional blood samples of up to a maximum of 100 ml, which is considered a minimal risk to the patient.

In conclusion, the risk due to methods and measurements in the present study is considered to be low and a positive risk-benefit is assessed.

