8.1.3 Nature and Content of Container(s)

Polyethylene plastic bottle (Ecoflac plus®), 500 mL

Ready-to-use container for single use only. The Investigational Products should be administered immediately after connecting the container to the giving set.

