8.2 Posology and Method of Administration

8.2.1 Dosage

Administration of the Investigational Products i.e. Gelofusine® Balanced + Sterofundin® ISO or Gelafundin® 4% + Sodium Chloride 0.9% in a blinded manner will be controlled individually by measuring CVP and MAP. The administration will be performed intravenously, starting preoperatively before induction of anesthesia. The following targets and triggers as in clinical routine apply:

The **TARGETS** for volume replacement are defined as:

- Central venous pressure between 10 and 14 mmHg (10 mmHg ≤ CVP ≤ 14 mmHg) minus PEEP after treatment with vasoactive agent

and

- Mean arterial pressure greater than 65 mmHg (MAP > 65 mmHg)

TRIGGERS for infusion of gelatines during surgery and postoperatively are:

- Central venous pressure (CVP) < 10 mm Hg minus PEEP

and

- Mean arterial pressure (MAP) < 65 mm Hg

The crystalloid : colloid ratio is 1 : 1 intra- and postoperatively. The first bottle is the crystalloid followed by the colloid and alternating thereafter. The starting infusion rate of either crystalloid or colloid is 5 mL/kg body weight (broca)/h and will be controlled by using an Infusomat.

The above specifications for crystalloid : colloid ratio and infusion rates are recommendations that ought to be met. However, the rates have to be adjusted according to the individual patient's need as defined by the above targets and triggers, up to a maximum of 5 mL/kg body weight (broca)/h for the crystalloids and of 20 mL/kg body weight (broca)/h for the colloids, as considered necessary by the investigator to stabilize the hemodynamics.

Postoperatively the investigational products will be given according to the patient's need.

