11.2.2 Reporting of Serious Adverse Events and Unexpected Adverse Reactions

All SAEs, whether or not deemed Investigational Product-related or expected must be reported to the Sponsor by telephone within 24 hours (one working day) of the Investigator becoming first knowledge:

Contact Name: see "Responsibilities and Addresses (section 1)

A written report must follow within five working days and is to include a full description of the event and sequelae, in the format detailed by the Serious Adverse Event reporting form provided by the Sponsor (see Appendix 3).

The Sponsor will notify the competent authorities, IECs and all investigators concerned of suspected SARs which are unexpected (SUSARs) in line with pertinent legal requirements.

While reporting adverse events, all pertinent data protection legislation must be adhered to.

Exempted from reporting within 24 hours are all SAEs which occurred before treatment with the gelatine component of the investigational regimen (bottle number 2), i.e. from induction of anesthesia until start of second bottle of investigational product treatment.

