- Immediate stop of infusion as soon as there are any signs of adverse reactions.

Emergency treatment of anaphylactoid reactions follows established schedules, depending on the severity of the reaction. It cannot be predicted by any test procedure which patients are likely to experience anaphylactoid reactions, nor is it possible to foresee the course and severity of any such reaction.

Anaphylactoid reactions caused by gelatin solutions may either be histamine mediated or histamine independent. Histamine release can be prevented by the use of a combination of H1- and H2 receptor blockers.

Prophylactic administration of corticosteroids has not proven effective.

Adverse reactions may occur in conscious and anesthetized patients. In the acute phase of volume deficiency shocks so far no anaphylactoid reaction has ever been reported.

Sterofundin® ISO:

Overdose or too fast administration may lead to water and electrolyte (including acetate, malate) overload with respective signs and symptoms as described in SmPC section "Overdose".

Gastrointestinal disorders:

Rare: Although oral magnesium salts stimulate peristalsis, paralytic ileus has been rarely reported after intravenous infusion of magnesium sulphate.

General disorders and administration site conditions:

Adverse reactions may be associated with the technique of administration including febrile response, infection at the site of injection, local pain or reaction, vein irritation, venous thrombosis or phlebitis extending from the site of injection and extravasation.

Immune system disorders

Not known: Hypersensitivity reactions characterized by urticaria have been occasionally described after the intravenous administration of magnesium salts.

Sodium Chloride 0.9%:

Overdose may result in hypernatremia, hyperchloremia, overhydration, hyperosmolality of the serum, and metabolic acidosis.

Administration of larger amounts may lead to hypernatremia and hyperchloremia (see also SmPC section "Overdose").

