11.5 Pregnancies

Not applicable, because the study is performed in the operation room and the ICU / IMC.

12 STUDY SCHEDULE**12.1 Procedures at Each Visit**

Pre-operatively:

- Verification of inclusion and exclusion criteria, including informed consent
- Blood samples for laboratory evaluation of electrolyte and coagulation status
- Urine sample in women of child bearing potential for pregnancy testing
- Demographic data, history
- Apfel-Score
- Pre-operative medication / therapy as medically indicated and standardized (including pre-operative fasting time)

Pre-anesthesia:

- Randomization (i.e. supply of blinded study samples)
- Set of catheters (e.g. arterial / central venous catheter)
- Baseline laboratory and hemodynamics
- Blood sampling for baseline laboratory evaluation
- Baseline ROTEM and baseline platelet aggregation
- Administration of first bottle of investigational products, i.e. crystalloid component
- Drug monitoring and tolerance
- Induction of anesthesia
- Concomitant medication and therapy (including concomitant medication and therapy prior induction of anesthesia; including blood products acc. to trigger)
- Adverse events/ reactions

After induction of anesthesia/prior surgery :

- Administration of investigational products
- Time on ventilator
- Final positioning of patient in operating theatre
- Set of urinary catheter for urine sampling
- Hemodynamics
- Blood sampling for laboratory evaluation
- Drug monitoring and tolerance
- Concomitant medication and therapy (including concomitant medication and therapy prior induction of anesthesia; including blood products acc. to trigger)
- Adverse events / reactions

During surgery :

- Administration of investigational products for volume replacement
- Surgery related data
- Intraoperative hemodynamics (every 15 min; CVP minus PEEP and MAP serve as trigger for IP-administration)
- Blood sampling for laboratory evaluation (blood gas analysis every 15 minutes, recovery room hourly)
- Drug monitoring and tolerance
- Recording of blood loss (drainage blood loss and estimated blood loss)
- if applicable, blood product administration
- Time on ventilation
- Concomitant medication and therapy
- Adverse events / reactions

End of surgery:

- Administration of investigational products for volume replacement according to algorithm
- Surgery related data
- Hemodynamics
- Blood sampling for laboratory evaluation
- Drug monitoring and tolerance

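### Protocol section 11.2.2 waives 24-hour reporting for every SAE between induction and bottle 2, including those possibly related to bottle 1, which is itself an investigational product

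*Protocol*

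**What the plan says.** Section 11.2.2 sets a general rule: every SAE, related or not and expected or not, goes to the sponsor by telephone within 24 hours, which the section equates with one working day. It continues: "A written report must follow within five working days". The section closes with the exemption: "Exempted from reporting within 24 hours are all SAEs which occurred before treatment with the gelatine component of the investigational regimen (bottle number 2"), a period then spelled out as "from induction of anesthesia until start of second bottle of investigational product treatment".

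Other sections fix what bottle 1 is:

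- Section 4.3: "The Investigational Products (IPs) Sterofundin® ISO, Gelafundin® 4% and Sodium Chloride 0.9% are registered". Both crystalloids are in that list.
- Section 12.1, pre-anaesthesia step: "Administration of first bottle of investigational products, i.e. crystalloid component".
- Section 11.4, on Sterofundin ISO: "Hypersensitivity reactions characterized by urticaria have been occasionally described after the intravenous administration of magnesium salts".
- Section 8.1.3, container: "Polyethylene plastic bottle (Ecoflac plus®), 500 mL".
- Section 8.2.1 sets a starting rate of 5 mL/kg (Broca)/h and lets rates be adjusted "up to a maximum of 5 mL/kg body weight (broca)/h for the crystalloids and of 20 mL/kg body weight (broca)/h for the colloids".

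**The concern.** The exemption treats the time before gelatine as though no study treatment had been given. In fact bottle 1 starts immediately before induction (8.2.3) and is part of the randomised regimen. A serious event attributed to it after induction is exempt in the same way as one due to an anaesthetic drug. The same section makes the sponsor responsible for passing SUSARs to authorities, ethics committees and investigators, and the sponsor cannot do that before it knows of the event. No DSMB is appointed (17.1.3), so the sponsor's own awareness carries more weight.

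The second weakness is where the exemption stops. A waiver meant for induction events would naturally end with induction or at incision. This one ends when a bottle is changed, which may happen after surgery has begun.

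**Working it through.** **1. Is bottle 1 study treatment?** Sections 4.3 and 12.1 say so directly. The composition table in 8.1.1 shows that it differs between arms: Sterofundin ISO has chloride 127 mmol/L with acetate, malate, potassium, calcium and magnesium, while NaCl 0.9% has chloride 154 mmol/L and none of these. Section 17.8 makes the SmPCs of all the investigational products the reference for expectedness, so the protocol itself foresees assessing reactions to the crystalloid.

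**2. Does the exemption spare related events?** No. It covers all SAEs in the window. The causality codes in 11.1.6 are available but are not used here.

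**3. Are the limits of the window clear?** Not fully. The main clause covers everything before gelatine, including bottle 1 time before induction. The explanatory clause starts only at induction. Neither gives a time limit or mentions incision.

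**4. How long might bottle 1 run?** Inputs: 500 mL (8.1.3), crystalloid ceiling 5 mL/kg/h, equal to the starting rate (8.2.1), and assumed Broca weights of 50, 70 and 90 kg. Run time = 500 / (5 × weight), if the bottle is infused in full at the ceiling:

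| Broca weight | Run time |
|---|---|
| 90 kg | 500/450 = 1.11 h |
| 70 kg | 500/350 = 1.43 h |
| 50 kg | 500/250 = 2.00 h |

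**5. Could that reach past incision?** The protocol gives neither the lead time from starting bottle 1 to induction nor the time from induction to incision, so both are assumed. If bottle 2 follows when bottle 1 is empty, exempt time after incision = run time − lead time − induction-to-incision time:

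- Middle case, 70 kg, 15 min and 45 min: 1.43 − 0.25 − 0.75 = 0.43 h, about 26 min.
- High case, 50 kg, 0 and 30 min: 2.00 − 0 − 0.50 = 1.50 h.
- Low case, 90 kg, 30 and 60 min: 1.11 − 0.50 − 1.00 is below zero, so none.

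**6. What is lost?** The telephone report within one working day. The written report is not expressly waived. If it applies, the latest date is five working days, normally about 7 calendar days. At the planned 64 patients in one year, 64/52 = 1.2 further patients would enter in that week, against 64/365 = 0.2 in one day. These are upper limits, since a site may report sooner.

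**The case against.** The case for leaving the text alone has substance. Only the 24-hour report is waived: section 11.2.1 still requires every AE in the CRF, and neither the written report nor the SUSAR duty is set aside. Both crystalloids are registered and used in line with their SmPCs. The main named risk is the anaphylactoid reaction to gelatine (11.4), and full reporting begins when gelatine does. Keeping induction events out of expedited reporting may be deliberate. The hypersensitivity cited for Sterofundin ISO is urticaria, a listed reaction. All of this stands and limits the size of the point. It does not explain why an event judged related to an investigational product should be exempt, and the protocol gives no reason.

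A reader might go further in three ways that the protocol does not support:

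- **The run times are minimum durations.** They are not. Section 8.2.1 calls the ratio and rates recommendations, and the labels (8.3) require ascending order and provide for discarding remainders. Nothing requires bottle 1 to be empty before bottle 2 starts.
- **The window can stay open for hours until the CVP and MAP triggers are met.** Section 8.2.1 lists those triggers for gelatine, but the alternating sequence in the same section and the synopsis rule that one crystalloid bag implies one colloid bag favour a simple sequence. The scheduled gelatine need of at least 15 mL/kg (7.2) also makes long windows uncommon.
- **The stopping rule is undermined.** Section 7.4.1 names severe bleeding and anaphylactic reactions and acts at 7 patients, but does not say that the count relies on telephoned SAEs. Blood loss is documented in any case (10.2.1).

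**Conclusion.** The point holds, at minor to moderate weight. What the text establishes without assumptions is that every SAE between induction and bottle 2 escapes 24-hour reporting, whatever its suspected cause, although bottle 1 is a randomised investigational product with listed reactions. That the window may extend past incision is a conditional finding. It rests on full infusion at the ceiling rate, on the assumed weights, and on an induction-to-incision time that the protocol does not state; the range includes no overlap at all. Few SAEs are likely to fall in the window. No between-arm bias, no effect on base excess or chloride, and no quantified effect on the stopping rule is claimed.

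**What to change.** Amend section 11.2.2 in three respects:

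1. **Relatedness (the main change).** Limit the exemption to SAEs not judged at least possibly related to any investigational product, using the codes in 11.1.6. State also how events coded not assessable are handled; keeping them under the 24-hour rule is the cautious choice.
2. **End of the window.** Let the exemption run from induction to skin incision or the start of bottle 2, whichever is earlier. Incision time is already recorded (10.3). This change alone would not be enough, because reactions to bottle 1 before incision would stay exempt.
3. **Written report.** State that the report within five working days still applies to exempt SAEs.

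The cost is one or two sentences, a short instruction to the two sites and a few more expedited reports. Dosing, bottle order, labels and assessments do not change.

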11.3 Adverse Event follow-up procedures

Adverse Events will be followed up throughout the course of the clinical trial.

11.4 Potential Risks and Potential Adverse Events

The proposed treatment is in line with normal procedures in abdominal surgery . However, the active substance of Gelofusine® Balanced, gelatine polysuccinate (= modified fluid gelatine), is a well-known active substance in the field of volume replacement over several decades. The difference between the well known product Gelafundin® 4% and the new gelatine solution Gelofusine® Balanced is the composition of the electrolyte carrier solution. This, in turn, represents a composition of electrolytes close to the composition of the blood plasma and is comparable with the carrier solution of other balanced gelofusine solutions like Isoplex® 4% or Geloplasma® and HES solutions like Tetraspan®. For the new gelatine solution Gelofusine® Balanced the same adverse drug reactions as for Gelafundin® 4% will apply.

According to the SmPCs for Gelafundin® 4%, for Gelafundin ISO 40 mg/ml, for Sterofundin® ISO and for Sodium chloride 0.9% the following adverse drug reactions are described:

Gelafundin ISO 40 mg/ml / Gelafundin® 4%:

Although anaphylactoid reactions are rare these are the most common side effects of gelofusine solutions.

Immune system disorders

Rare: Anaphylactoid reactions (all grades)

After the administration of gelatine solution infusions, just as of any colloidal volume substitutes, anaphylactoid reactions of varying degrees of severity may occur. These reactions manifest as cutaneous eruptions and may proceed over sudden flushing of

the face and neck to a drop in blood pressure, shock, cardiac and respiratory arrest. Severe anaphylactoid reactions (grade III or IV) are very rare (incidence < 1 : 10 000). Patients receiving gelatine solutions must be continuously observed for the occurrence of anaphylactoid reactions.

Gastrointestinal disorders

Uncommon: Transient mild nausea or abdominal pain

General disorders

Uncommon: Transient mild rise of body temperature

The following general guidelines for the prophylaxis of adverse reactions apply:

- Adequate information of physicians and nursing staff about the type and severity of possible adverse reactions that may be encountered after the administration of a colloidal volume substitute.
- Careful observation of the patient during infusion, especially while the first 20 – 30 ml of the solution are being infused.
- Immediate availability of all equipment and medication for cardio-pulmonary resuscitation.
- Immediate stop of infusion as soon as there are any signs of adverse reactions.

Emergency treatment of anaphylactoid reactions follows established schedules, depending on the severity of the reaction. It cannot be predicted by any test procedure which patients are likely to experience anaphylactoid reactions, nor is it possible to foresee the course and severity of any such reaction.

Anaphylactoid reactions caused by gelatin solutions may either be histamine mediated or histamine independent. Histamine release can be prevented by the use of a combination of H1- and H2 receptor blockers.

Prophylactic administration of corticosteroids has not proven effective.

Adverse reactions may occur in conscious and anesthetized patients. In the acute phase of volume deficiency shocks so far no anaphylactoid reaction has ever been reported.

Sterofundin® ISO:

Overdose or too fast administration may lead to water and electrolyte (including acetate, malate) overload with respective signs and symptoms as described in SmPC section "Overdose".

Gastrointestinal disorders:

Rare: Although oral magnesium salts stimulate peristalsis, paralytic ileus has been rarely reported after intravenous infusion of magnesium sulphate.

General disorders and administration site conditions:

Adverse reactions may be associated with the technique of administration including febrile response, infection at the site of injection, local pain or reaction, vein irritation, venous thrombosis or phlebitis extending from the site of injection and extravasation.

Immune system disorders

Not known: Hypersensitivity reactions characterized by urticaria have been occasionally described after the intravenous administration of magnesium salts.

Sodium Chloride 0.9%:

Overdose may result in hypernatremia, hyperchloremia, overhydration, hyperosmolality of the serum, and metabolic acidosis.

Administration of larger amounts may lead to hypernatremia and hyperchloremia (see also SmPC section "Overdose").

11.5 Pregnancies

Not applicable, because the study is performed in the operation room and the ICU / IMC.

12 STUDY SCHEDULE**12.1 Procedures at Each Visit**

Pre-operatively:

- Verification of inclusion and exclusion criteria, including informed consent
- Blood samples for laboratory evaluation of electrolyte and coagulation status
- Urine sample in women of child bearing potential for pregnancy testing
- Demographic data, history
- Apfel-Score
- Pre-operative medication / therapy as medically indicated and standardized (including pre-operative fasting time)

Pre-anesthesia:

- Randomization (i.e. supply of blinded study samples)
- Set of catheters (e.g. arterial / central venous catheter)
- Baseline laboratory and hemodynamics
- Blood sampling for baseline laboratory evaluation
- Baseline ROTEM and baseline platelet aggregation
- Administration of first bottle of investigational products, i.e. crystalloid component
- Drug monitoring and tolerance
- Induction of anesthesia
- Concomitant medication and therapy (including concomitant medication and therapy prior induction of anesthesia; including blood products acc. to trigger)
- Adverse events/ reactions

After induction of anesthesia/prior surgery :

- Administration of investigational products
- Time on ventilator
- Final positioning of patient in operating theatre
- Set of urinary catheter for urine sampling
- Hemodynamics
- Blood sampling for laboratory evaluation
- Drug monitoring and tolerance
- Concomitant medication and therapy (including concomitant medication and therapy prior induction of anesthesia; including blood products acc. to trigger)
- Adverse events / reactions

During surgery :

- Administration of investigational products for volume replacement
- Surgery related data
- Intraoperative hemodynamics (every 15 min; CVP minus PEEP and MAP serve as trigger for IP-administration)
- Blood sampling for laboratory evaluation (blood gas analysis every 15 minutes, recovery room hourly)
- Drug monitoring and tolerance
- Recording of blood loss (drainage blood loss and estimated blood loss)
- if applicable, blood product administration
- Time on ventilation
- Concomitant medication and therapy
- Adverse events / reactions

End of surgery:

- Administration of investigational products for volume replacement according to algorithm
- Surgery related data
- Hemodynamics
- Blood sampling for laboratory evaluation
- Drug monitoring and tolerance
- Recording of blood loss (drainage blood loss and estimated blood loss)
- if applicable, blood product administration
- Time on ventilation
- Concomitant medication and therapy

- Intraoperative diuresis: cumulated diuresis from start of anesthesia until end of surgery
- Adverse events / reactions

Admission to ICU / IMC:

- Administration of investigational products for volume replacement according to algorithm
- Hemodynamics
- Blood and urine sampling for laboratory evaluation
- Drug monitoring and tolerance
- Administration of blood products, if applicable
- Recording of secondary bleeding, if applicable
- Time on ventilation, if applicable
- Concomitant medication and therapy
- Adverse events / reactions
- Clinical outcome

6 hours after end of surgery:

- Administration of investigational products for volume replacement according to algorithm
- Hemodynamics
- Blood and urine sampling for laboratory evaluation
- Drug monitoring and tolerance
- Administration of blood products, if applicable
- Recording of secondary bleeding, if applicable
- Time on ventilation
- Concomitant medication and therapy
- Adverse events / reactions

12 hours after end of surgery:

- End of administration of investigational products for volume replacement according to algorithm
- Hemodynamics
- Blood and urine sampling for laboratory evaluation
- Drug monitoring and tolerance
- Administration of blood products, if applicable
- Recording of secondary bleeding, if applicable
- Postoperative diuresis (admission ICU / IMC – 12 hours after end of surgery)

- Time on ventilation
- Concomitant medication and therapy
- Length of stay (ICU / IMC)
- Adverse events / reactions
- Study termination

